### Treatment Day 1 (Visit 2)

This visit will be performed on the 1st prasugrel MD administration (Day 1). The following examinations/procedures will be performed:

- Confirmation of inclusion / exclusion criteria.
- Confirmation of subject eligibility
- Physical examination
- Vital signs (including blood pressure)
- Laboratory (platelet function) to be done immediately before first dose of prasugrel MD + aspirin administration of Day 1
- Laboratory (hematology, biochemistry)
- Recording of bleeding events
- Recording of major adverse cardiovascular events
- Recording of all cause death
- Study drug dispensing (prasugrel 3.75 mg)
- Recording of adverse events
- Recording of concomitant medication

**Treatment week 4 (Visit 3, Day 28 ± 14). End of Period 1**

This visit will be performed 4 weeks after the 1st prasugrel MD administration, as the end of the Period 1. The following examinations/procedures will be performed:

- Physical examination
- Vital signs (including blood pressure)
- Laboratory (hematology, biochemistry)
- Laboratory (platelet function) to be done immediately before the daily dose of prasugrel MD + aspirin administration of Visit 3
- Blood sample for CYP2C19 genotyping (before prasugrel MD + aspirin administration of Visit 3)
- Electrocardiogram
- Recording of bleeding events
- Recording of major adverse cardiovascular events
- Recording of all cause death
- Study drug dispensing (prasugrel 3.75 mg)
- Recording of adverse events
- Recording of concomitant medication

**Treatment week 16 (Visit 4, Day 112 ± 14)**

This visit will be performed 16 weeks after the 1st prasugrel MD administration. The following examinations/procedures will be performed:

- Physical examination
- Vital signs (including blood pressure)
- Laboratory (hematology, biochemistry)
- Recording of bleeding events
- Recording of major adverse cardiovascular events
- Recording of all cause death
- Study drug dispensing (prasugrel 3.75 mg)
- Recording of adverse events
- Recording of concomitant medication

**Treatment week 28 (Visit 5, Day 196 ± 28). End of Period 2**

This visit will be performed 28 weeks after the 1st prasugrel MD administration, as the end of the Period 2. The following examinations/procedures will be performed:

- Physical examination

- Vital signs (including blood pressure)
- Laboratory (hematology, biochemistry), serum pregnancy test (for women of childbearing potential)
- Electrocardiogram
- Recording of bleeding events
- Recording of major adverse cardiovascular events
- Recording of all cause death
- Recording of adverse events
- Recording of concomitant medication

**Optional treatment maximum 12 months of P2Y12 inhibitor treatment after ACS underwent PCI (Visit 6, Day 365 - 28). End of Period 2**

This visit is optional and will be based on investigator's discretion, and will be performed up to maximum overall 12 months of P2Y12 inhibitor treatment after ACS underwent PCI, as the end of the Period 2. The following examinations/procedures will be performed:

- Physical examination
- Vital signs (including blood pressure)
- Laboratory (hematology, biochemistry), serum pregnancy test (for women of childbearing potential)
- Electrocardiogram
- Recording of bleeding events
- Recording of major adverse cardiovascular events
- Recording of all cause death
- Recording of adverse events
- Recording of concomitant medication

**Early Termination**

In case of an early termination after 1st prasugrel MD administration and before treatment at visit 5 (week 28), the same procedures planned for the treatment at visit 5 (week 28) should be performed.

### Unscheduled Visit

Unscheduled visits may be arranged following investigators' discretion for adverse event findings identified either at the end of study or during the follow-up period. The examinations/procedures may include:

- Physical examination
- Vital signs
- Laboratory (hematology, biochemistry), serum pregnancy test (for women of childbearing potential)
- Electrocardiogram, heart rate, blood pressure
- Recording of adverse events
- Recording of concomitant medication

### Telephone Contacts

Sites will maintain telephone contacts with subjects during the study as reminders for the study logistics, including the safety assessment during follow-up.

## 8.4.3 Efficacy Variables

### 8.4.3.1 PERIOD 1 (4 weeks)

#### 8.4.3.1.1 Primary Variables

The primary variable will be the mean change in the P2Y12 reaction unit (PRU) value assessed with VerifyNow® from baseline to the end of the 4-week MD treatment period, after switching from clopidogrel MD to prasugrel MD.

#### 8.4.3.1.2 Secondary Variables

Secondary variables of the period 1 will assess both efficacy and safety:

Efficacy (antiplatelet effect):

- Percentage of High on-Treatment Platelet Reactivity (HTPR) defined as PRU > 235.
- Percentage of platelet inhibition at the end of the 4-week MD treatment period, after switching from clopidogrel MD to prasugrel MD.

Safety:

- Major bleeding events (non-coronary artery bypass grafting [CABG] thrombolysis in myocardial infarction (TIMI) major) after 4 MD treatment weeks.
- Minor and clinically relevant bleeding events after 4 MD treatment weeks.
- Major adverse cardiovascular events (MACE) including cardiovascular death, non-fatal myocardial infarction (MI), non-fatal stroke, stent thrombosis and revascularization after 4 MD treatment weeks.

- All cause deaths after 4 MD treatment weeks.
- Adverse events after 4 MD treatment weeks.

### **8.4.3.2 PERIOD 2 (+24 weeks [optionally up to a maximum 12 months of P2Y12 inhibitor treatment after ACS underwent PCI, based on investigator's discretion])**

#### **8.4.3.2.1 Primary Variables**

The primary variable will be the incidence of major bleeding events (non-coronary artery bypass grafting [CABG] thrombolysis in myocardial infarction (TIMI) major) after 28 MD treatment weeks or up to maximum 12-month P2Y12 inhibitor treatment after ACS underwent PCI.

#### **8.4.3.2.2 Secondary Variables**

Secondary variables of the period 2 will assess just safety in terms of the incidence of:

- Minor and clinically relevant bleeding events after 28 MD treatment weeks (optional maximum 12-month P2Y12 inhibitor treatment after ACS underwent PCI).
- Major adverse cardiovascular events (MACE) including cardiovascular death, non-fatal myocardial infarction (MI), non-fatal stroke, stent thrombosis and revascularization after 28 MD treatment weeks (optional maximum 12-month P2Y12 inhibitor treatment after ACS underwent PCI).
- All cause deaths after 28 MD treatment weeks (optional maximum 12-month P2Y12 inhibitor treatment after ACS underwent PCI).
- Adverse events after 28 MD treatment weeks (optional maximum 12-month P2Y12 inhibitor treatment after ACS underwent PCI).

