###### **Secondary variables:**

Incidence of events (minor or clinically relevant bleeding events, major adverse cardiovascular events) after 28 MD treatment weeks up to maximum 12-month P2Y12 inhibitor treatment after ACS underwent PCI, based on investigator's discretion, will be summarized with their corresponding 95% confidence interval, including median times to events as per Kaplan-Meier estimates.

Percentage of all cause deaths and adverse events after 28 MD treatment weeks (optionally up to a maximum 12 months of P2Y12 inhibitor treatment after ACS underwent PCI, based on investigator's discretion) will be summarized with their corresponding 95% confidence interval.

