## 8.1. Inclusion Criteria

Subjects will be eligible for inclusion into the study only if all of the following criteria are met:

- (1) Subject who has provided signed informed consent.
- (2) Subject of either sex aged  $\geq 20$  years old at the informed consent date
- (3) Subject's weight of at least 50 kg at the time of screening
- (4) Subject with previous diagnosis of ACS (unstable angina [UA], non-ST elevation myocardial infarction [NSTEMI], or ST elevation myocardial infarction [STEMI]) who has undergone PCI and was treated with either:
  - clopidogrel maintenance dose (MD) of 75 mg once daily and aspirin 81-100 mg per day for 2-8 weeks following clopidogrel loading dose (LD) of 300 mg or 600 mg at the time of PCI
  - or ticagrelor MD of 90 mg bid and aspirin 81-100 mg per day for 1-4 weeks and switching to clopidogrel maintenance dose (MD) of 75 mg once daily and aspirin 81-100 mg per day for 2-4 weeks (either directly or via clopidogrel loading dose [LD] of 300 mg or 600 mg) following ticagrelor LD of 180 mg at the time of PCI
  - or clopidogrel maintenance dose (MD) 75 mg once daily and aspirin 81-100 mg per day for 2-8 weeks following ticagrelor LD of 180 mg at the time of PCI

- or based on investigator's judgement with at least 2 weeks continues use of clopidogrel MD and aspirin 81-100 mg per day before switching to prasugrel and maximum 8 weeks P2Y12 inhibitors MD treatment (prasugrel is not allowed)

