- If a subject has a pre-existing episodic condition (e.g., asthma, epilepsy) any occurrence of an episode should only be captured as a AE if the episodes become more frequent, serious or severe in nature, that is, investigators should ensure that the AE term recorded captures the change in the condition from Baseline (e.g., “worsening of...”).
- If a subject has a degenerative concurrent condition (e.g., cataracts, rheumatoid arthritis), worsening of the condition should only be captured as an AE if occurring to a greater extent to that which would be expected. Again, investigators should ensure that the AE term recorded captures the change in the condition (e.g., “worsening of...”).

Worsening of AEs:

- If the subject experiences a worsening or complication of an AE after starting administration of the study medication, the worsening or complication should be recorded appropriately as an AE. Investigators should ensure that the AE term recorded captures the change in the condition (e.g., “worsening of...”).
- If the subject experiences a worsening or complication of an AE after any change in study medication, the worsening or complication should be recorded as a new AE. Investigators should ensure that the AE term recorded captures the change in the condition (e.g., “worsening of...”).

Changes in severity of AEs:

- If the subject experiences changes in severity of an AE, the event should be captured once with the maximum severity recorded.

Preplanned surgeries or procedures:

- Preplanned procedures (surgeries or therapies) that were scheduled prior to signing of informed consent are not considered AEs. However, if a preplanned procedure is performed early (e.g., as an emergency) due to a worsening of the pre-existing condition, the worsening of the condition should be captured appropriately as an AE. Complications resulting from any planned surgery should be reported as AEs.

Elective surgeries or procedures:

- Elective procedures performed where there is no change in the subject's medical condition should not be recorded as AEs, but should be documented in the subject's source documents. Complications resulting from an elective surgery should be reported as AEs.

Insufficient clinical response (lack of efficacy):

- Insufficient clinical response, efficacy, or pharmacologic action, should NOT be recorded as an AE. The investigator must make the distinction between exacerbation of pre-existing illness and lack of therapeutic efficacy.

Overdose:

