### 9.1.3 Serious Adverse Event

Serious adverse events are defined as any untoward medical occurrence that at any dose:

- result in subject's death.
- are life-threatening.
- result in permanent or significant disability/incapacity.
- cause hospital admission or prolong hospital stay.
- result in congenital anomalies or birth defects.
- medically important condition that may jeopardize the subject or may require intervention to prevent any of the outcomes listed above. Examples of such events are intensive treatment in an emergency room or at home for allergic bronchospasm; blood dyscrasias, or convulsions that do not result in hospitalization; or development of drug dependency or drug abuse.

NOTE: The term "life-threatening" in the definition of "serious" refers to any adverse event that places the subject, in the view of the investigator, at immediate risk of death from the event as it

occurred, i.e., it does not include an event that, had it occurred in a more severe form, might have caused death.

An overnight stay in the hospital that is only due to transportation, organization or accommodation problems and without medical background does not need to be handled/documentated as a SAE. Hospitalizations due to surgical procedures for pre-existing conditions that have been planned before enrolment of the subject are not considered SAEs.

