## 11.1.4.2 Secondary Safety Analysis

### 11.1.4.2.1 PERIOD 1 (4 weeks)

Incidence of events after 4 MD treatment weeks (major bleeding events, minor or clinically relevant bleeding events, major adverse cardiovascular events) will be summarized with their corresponding 95% confidence interval, including median times to events as per Kaplan-Meier estimates.

Percentage of all cause deaths and adverse events after 4 MD treatment weeks will be summarized with their corresponding 95% confidence interval.

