### 11.1.4.2.2 PERIOD 2 (+24 weeks [optionally up to a maximum 12 months of P2Y12 inhibitor treatment after ACS underwent PCI, based on investigator's discretion])

Incidence of events after 28 MD treatment (optional maximum 12-month P2Y12 inhibitor treatment period after ACS underwent PCI) (minor or clinically relevant bleeding events, major adverse cardiovascular events, stent thrombosis and revascularization) will be summarized with their corresponding 95% confidence interval, including median times to events as per Kaplan-Meier estimates.

Percentage of all cause deaths and adverse events after 28 MD treatment (optional maximum 12-month P2Y12 inhibitor treatment period after ACS underwent PCI) will be summarized with their corresponding 95% confidence interval.

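### MACE counts revascularization without a qualifier, so procedures scheduled before consent could be counted, and the Period 2 analysis text leaves the composite open to two readings

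*Combined protocol and SAP*

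**What the plan says.** The Period 2 definition in section 8.4.3.2.2 reads "Major adverse cardiovascular events (MACE) including cardiovascular death, non-fatal myocardial infarction (MI), non-fatal stroke, stent thrombosis and revascularization". The Period 1 definition in 8.4.3.1.2 has the same five components and ends "non-fatal stroke, stent thrombosis and revascularization after 4 MD treatment weeks". The Summary endpoints and sections 6.2.1.2 and 6.2.2.2 repeat the list. None of these places says whether the revascularization must be unplanned, urgent, ischaemia-driven or of the target vessel. Section 8.4.1 has subsections on bleeding events and all-cause deaths but none on MACE, and no event adjudication is described.

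Entry is early after the index procedure. One qualifying route in section 8.1 is clopidogrel maintenance "for 2-8 weeks following clopidogrel loading dose (LD) of 300 mg or 600 mg at the time of PCI", and the other routes also allow at most 8 weeks of prior maintenance treatment. Section 8.2 has no exclusion for a pending procedure. Section 8.4.2 and the schedule in 18.1 record MACE at every visit from Day 1.

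The adverse event rules do make a distinction. Section 9.1.2 states: "Preplanned procedures (surgeries or therapies) that were scheduled prior to signing of informed consent are not considered AEs". If such a procedure is brought forward because the condition worsens, the worsening is captured as an AE. The same section leaves elective procedures out of AE recording when the subject's condition has not changed. Section 9.1.3 adds: "Hospitalizations due to surgical procedures for pre-existing conditions that have been planned before enrolment of the subject are not considered SAEs".

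The analysis lists differ:
- Section 11.1.4.2.1 (Period 1): "major bleeding events, minor or clinically relevant bleeding events, major adverse cardiovascular events".
- Section 11.1.4.2.2 (Period 2): "minor or clinically relevant bleeding events, major adverse cardiovascular events, stent thrombosis and revascularization".
- Summary, Period 2 secondary variables: "Incidence of events (minor or clinically relevant bleeding events, major adverse cardiovascular events) after 28 MD treatment weeks".

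**The concern.** A second procedure on another lesion may still be pending when a subject enters a few weeks after PCI for ACS. Taken literally, the MACE bullet counts that procedure when it happens, even if it was booked before consent and went ahead as booked. The protocol would then report a major adverse cardiovascular event for which its own rules call for no adverse event. The study is non-comparative, so no control arm carries the same scheduled procedures and would show how much of the incidence they account for.

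The second issue is what the Period 2 analysis means by MACE. The wording of 11.1.4.2.2 allows the five-component composite with two components reported again, or a composite without those two. An analyst following the second reading would produce a Period 2 figure not comparable with the Period 1 figure.

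**Working it through.** **The plan's own event figure.** Section 11.2 says 170 completers give an 82% chance of seeing at least one event of incidence 0.01. This reproduces: 1 - 0.99^170 = 0.8189. The enrolment figure also reproduces: 170 / (1 - 0.15) = 200. Neither depends on how MACE is defined, and the plan gives no expected MACE rate.

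**Comparison of the texts.**

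| Place | Stent thrombosis and revascularization |
|---|---|
| Summary endpoints, 6.2.1.2, 6.2.2.2, 8.4.3.1.2, 8.4.3.2.2 | inside MACE, both periods |
| 11.1.4.2.1 (Period 1 analysis) | not listed separately; MACE only |
| Summary, Period 2 analysis | not listed separately; MACE only |
| 11.1.4.2.2 (Period 2 analysis) | listed beside MACE |

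The definitions agree with each other. Section 11.1.4.2.2 is the only place that differs, and it does not say that the two components leave the composite. Both analysis sections call for Kaplan-Meier estimates, which fits a first-event analysis, but neither states a first-event rule.

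**Possible size.** Let m be the proportion with any other MACE and s the proportion with a planned revascularization during follow-up. Both are assumptions: m from 1% to 5%, s from 0% to 10%. If the two are independent and every planned procedure is counted,

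observed MACE = 1 - (1 - s)(1 - m).

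| s | m = 1% | m = 5% |
|---|---|---|
| 0% | 1.0% | 5.0% |
| 2% | 1 - 0.98 × 0.99 = 2.98% | 1 - 0.98 × 0.95 = 6.9% |
| 5% | 1 - 0.95 × 0.99 = 5.95% | 1 - 0.95 × 0.95 = 9.75% |
| 10% | 1 - 0.90 × 0.99 = 10.9% | 1 - 0.90 × 0.95 = 14.5% |

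With no pending procedures there is no inflation. At s = 2% and m = 5% the ratio is 6.9 / 5 = 1.38; at s = 5% and m = 1% it is 5.95 / 1, about 6.

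**Against the precision of the estimate.** Take 200 subjects, exact 95% intervals, and planned procedures simply added to other MACE:
- Other MACE 2% (4 events): 2.0% (0.5-5.0). With 5% planned (14 events): 7.0% (3.9-11.5).
- Other MACE 4% (8 events): 4.0% (1.7-7.7). With 5% planned (18 events): 9.0% (5.4-13.9).

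In both illustrations the inflated interval excludes the rate without planned procedures, so the effect could exceed sampling error.

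**The case against.** The strongest reply is that the MACE bullet should be read together with section 9.1.2. MACE is by name a class of adverse events. If a procedure scheduled before consent is not an adverse event, it should not be a major one either. The documents never mention staged procedures, so a reader who infers that the protocol makes each one a MACE goes further than the text. This stands: the wording permits the count but does not require it. It does not remove the problem, because nothing in the MACE definition refers to 9.1.2 and a site could reasonably record either way.

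A reader might also cite 9.1.3 as a second direct contradiction. Its wording covers hospitalization for surgical procedures planned before enrolment. Applying it to a percutaneous procedure is natural but not literal, so the point rests on 9.1.2, which covers surgeries or therapies.

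A reader might infer from 11.1.4.2.2 that the two periods report different composites. Since every definition is the same, the more natural reading is that two components are reported additionally. That leaves an ambiguity to close, not an established difference.

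Finally, section 11.1 defers full detail to a separate analysis plan approved before database closure. Neither that detail nor the eCRF is in the text reviewed, so an operational definition may exist elsewhere. A later plan could settle the composite. It could not reliably recover whether a procedure was scheduled before consent unless sites had recorded it.

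Whether to count all revascularization or only unplanned is partly the sponsor's choice. The documents do not show that the narrower endpoint was intended, but section 9.1.2 gives a basis for it.

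**Conclusion.** The concern holds as an ambiguity in a secondary endpoint that should be resolved. As written, the protocol could count a revascularization scheduled before consent and performed on schedule after Day 1 as MACE, and the Period 2 composite can be read in two ways.

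The size is unknown. Under the assumed ranges, observed MACE lies between 1-5% (no planned procedures) and 10.9-14.5% (planned procedures in 10% of subjects, all counted). A reader might pick out the roughly sixfold inflation, or conclude that scheduled care would drive the MACE rate. The documents support neither: the sixfold figure is one cell of a wholly assumed grid that also gives about 1.4 times and no inflation at all. Procedures completed before Day 1 do not enter the count.

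MACE is reported descriptively with a confidence interval, and no test or decision rests on it. The PRU change, TIMI major bleeding and the sample size are unaffected.

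**What to change.** 1. In the Summary, 6.2 and 8.4.3, align the MACE component with 9.1.2: exclude revascularizations scheduled before consent and performed as planned, and keep those brought forward because of worsening.
2. State how elective revascularizations scheduled after consent are handled, since 9.1.2 treats elective procedures separately.
3. Add a yes/no item to the eCRF for whether each revascularization was planned before consent, and report planned procedures separately so that no information is lost.
4. In 11.1.4.2.1 and 11.1.4.2.2, specify the same five-component MACE as a first-event composite in both periods, with each component, including stent thrombosis and revascularization, also listed separately. Bring the Summary into line.

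The cost is wording and one eCRF item. The downside is a slightly lower MACE count and the need for sites to document that a procedure was already scheduled at consent.

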### **8.4.4 Exploratory Variables**

The association CYP2C19 genotyping for available subjects (targeted 100 subjects) who have signed the pharmacogenomic informed consent form separately will be assessed as exploratory analysis.

## **8.5. Removal of Subjects from Therapy or Assessment**

### **8.5.1 Screening failures**

Subjects who signed the informed consent form and performed screening activities (either completely or partially) but not having started the 1st prasugrel MD treatment are considered screening failures.

If the subject is found to be not eligible at this visit, the investigator should complete the eCRF for screening visit only.

The primary reason for screen failure should be recorded in the eCRF using the following categories:

- AE.
- Did not meet inclusion criteria or did meet exclusion criteria.
- Significant protocol deviation.
- Lost to follow-up.
- Voluntary withdrawal, <specify reason>.
- Study termination.
- Other, <specify reason>.

Subject numbers assigned to subjects who fail screening should not be reused.

